Participants will be asked to fill out the STAI questionnaire to assess the level of anxiety prior to placement of the labor epidural catheter, and before knowing their group assignment. They will then complete the pre procedure questionnaire. This questionnaire asks about expectations she has for the labor epidural procedure. They will then be given the page of the Newest Vital Signs questionnaire with the Nutrition Facts, and be asked the 6 questions by the recruiter. Then they will be asked the Pain Catastrophizing Scale questionnaire with 13 statements, and asked to respond as directed by the instructions stated by the researcher. They will then be asked who their primary support person is. A form will be handed to that person to confidentially record if he/she would prefer to be present for the procedure. This form will be collected from the support person, and without the parturient aware of the support person's response, she will be asked for her preference with regard to the presence of a support person in

the room, which will be recorded on this form as well. Finally, she will be asked which ethnicity she most relates to, also to be recorded on this form.

After all these data have been collected, the parturient will be randomized as to whether her companion will be allowed in the room or will be asked to leave. This will not be communicated to the parturient until the time of the labor epidural catheter placement. When she requests the neuraxial labor analgesia, the provider placing the labor epidural catheter will be made aware of which group she has been randomized to, and will either ask the companion to leave for placement, or provide the companion a non-mobile chair to sit on in front of the parturient for placement of the labor epidural. The companion will be asked to remain in the chair. He/she will be asked to focus on the parturient. It will be emphasized that he/she must remain seated and will not be allowed to observe the procedure being performed. This is to prevent loss of consciousness in the companion, which has been documented in the literature (Devore and Asrani, 1978; Crosby and Halpern, 1989). One violation will result in a warning, and after a second the companion will be escorted out of the room and the participant will be removed from the study.

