Group sample sizes of 75 and 75 achieve 81% power to show a difference in means when there is a difference of 4.7 between the null hypothesis mean difference of 0.0 and the actual mean difference of -4.7 at the 0.050 significance level (alpha) using a two-sided Mann-Whitney-Wilcoxon Test.

The acquired data forms will be kept in folders with only the study ID number as an identifier. These folders will be placed in a secure, locked cabinet in the Office of the Section of Obstetrical Anesthesiology. Only those researchers directly analyzing these data will have access to the files. Any electronic communication regarding the study will be conducted using the secure Northwestern email service. Computerized data forms will be password protected. Only the study ID number will be used to identify participants during data analysis. The data will be stored until the completion of the study, including the final data analysis. Members of the anesthesia team collecting these data will be educated on the process prior to approaching prospective participants.

These data collected from each participant will include:

- STAI forms before and after epidural placement
- Pre and post procedure questionnaire
- VAS scoring of satisfaction and pain perception following the procedure
- Newest Vital Sign form completed before epidural placement
- Pain Catastrophizing Score form completed before epidural placement
- Relation of the support person to the parturient
- Support person and parturients preference completed before epidural placement
- Post procedure questionnaire from the Resident/Fellow Physician
- Post procedure questionnaire from the Attending Physician

PROVISIONS TO MONITOR THE DATA TO ENSURE THE SAFETY OF PARTICIPANTS:

N/A

WITHDRAWAL OF PARTICIPANTS:

Participants will be withdrawn from the study if the companion is required to leave due to violation of directions. These include entering the room before the procedure is completed if he/she is in the partner out group, getting up from the chair or attempting to watch the procedure after a warning in the partner in group. When a participant withdraws, data collected up to that point will be retained and analyzed at the end of the study to determine if there is an identifying characteristic that predisposes to inability to follow instructions for safe participation with the epidural procedure.

RISKS TO PARTICIPANTS:

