Participants will be recruited on the Labor and Delivery Ward 8th floor of Prentice Women's Hospital. They will be approached regarding participation if they meet inclusion criteria during chart review or initial pre-anesthesia interview. Both patients in spontaneous labor and those scheduled for induction of labor will be approached if they meet criteria. The GE Centricity computerized board that lists all active laboring parturients is available in the anesthesia work room for review of the current Labor and Delivery census. If the patient is nulliparous she will be approached by a member of the

research team with regard to enrollment in the study. No reimbursement will be offered for participation.

NUMBER OF LOCAL PARTICIPANTS:

A total of 150 participants will complete the study. Half of the participants (n=75) will be randomized to the “companion in the room” group and half (n=75) will be randomized to the “companion out of the room” group. We are anticipating minimal patients who enroll to become ineligible during the study, since the total duration of enrollment is likely less than a couple hours, however we will attempt to recruit 180 participants in total to allow for a 20% drop-out rate, either by choice or by protocol violation.

Resident Participation: A total of 64 participants

Attending Physician: A total of 30 participants

Companion: A total of 150 participants

CONFIDENTIALITY:

Data will be stored in a department server which is password protected. Each study subject will be assigned a study code number. The code will be used to link study data to patient identification (name) in a separate database. Subject data will be stored on secured password protected computers at Northwestern University and Department of Anesthesiology servers. Paper data will be completed by research study team members and will be entered into REDCap. The paper folders will be stored in Arkes Pavilion 10th floor Department of Anesthesiology administrative office via key card controlled front door and key controlled closet. Data access will be password protected and only available to study investigators via REDCap. REDCap access will be controlled by the Principal Investigator. Data both electronic and paper will be destroyed 5 years after manuscript preparation.

PROVISIONS TO PROTECT THE PRIVACY INTERESTS OF PARTICIPANTS:

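### The only test named, in a power statement tied to no endpoint, is an unadjusted Mann-Whitney test; as the test for satisfaction it is valid, but it leaves prognostic data collected before randomisation unused

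*Combined protocol and SAP*

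**What the plan says.** The power statement under DATA AND SPECIMEN MANAGEMENT opens with "Group sample sizes of 75 and 75 achieve 81% power to show a difference in means". It assumes a shift of 4.7 against a null of zero, and the test is given as "at the 0.050 significance level (alpha) using a two-sided Mann-Whitney-Wilcoxon Test". It does not say which endpoint or scale the 4.7 refers to, and it gives no SD. No other test is named anywhere, and none is linked to pain.

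STUDY ENDPOINTS makes maternal satisfaction primary and lists anxiety and pain among the secondary questions. Under PROCEDURES INVOLVED, satisfaction and pain are each recorded once, after placement, on a 0-100 mm VAS. Neither has a baseline value.

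The same section puts the following before randomisation: the STAI, the pre-procedure questionnaire ("This questionnaire asks about expectations she has for the labor epidural procedure"), the Newest Vital Sign, the Pain Catastrophizing Scale, the preferences of the woman and her companion, and ethnicity. The data list confirms a "Pain Catastrophizing Score form completed before epidural placement". Whether labor is induced or spontaneous is known from screening (INCLUSION AND EXCLUSION CRITERIA). Catastrophizing and labor onset reappear only in secondary questions about anxiety, never as adjustment variables for satisfaction or pain.

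**The concern.** A woman's anxiety, her tendency to catastrophize, what she expects of the procedure and how her labor began could all plausibly influence how satisfied she is with the placement and how painful she finds it. All are fixed before allocation, so adjusting for them is legitimate. A two-sample rank test leaves whatever variation they explain in the error term. In a trial planned at only 81% power, that may give away precision already paid for by the data collection.

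The second issue is pre-specification. With several candidate covariates and no stated model, any adjustment chosen after the results are seen would be open to the charge of selection. The plan also mentions no effect estimate or confidence interval for the arm comparison.

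**Working it through.** **Inputs from the protocol.** 75 per group, difference 4.7, two-sided alpha 0.05, Mann-Whitney test, power 81%.

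**Inputs assumed.** The SD (not stated), and R², the share of outcome variance explained by the covariates (not stated; taken from 0 to 0.20).

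**Step 1: reproduce the 81%.** Without an SD this cannot be done directly, so I solved for the SD that yields 81%:
- two-sample normal approximation: 10.14
- two-sample t-test: 10.08
- Mann-Whitney with normal data (efficiency 3/π): 9.84

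For the last of these:
- effective n = 75 × 3/π = 71.6 per group
- standard error = 9.84 × √(2/71.6) = 1.644
- noncentrality = 4.7/1.644 = 2.86
- power from the noncentral t = 81.0%

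A simulation of 20,000 trials with the actual Mann-Whitney test also gave 81.0%. For other distributions the required SD is larger: 10.56 for logistic and 12.37 for double-exponential data. The stated figure is therefore consistent with an SD near 10 and is not shown to be wrong.

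**Step 2: add the covariates.** In a linear model the residual SD becomes SD × √(1 − R²), so the noncentrality becomes 2.86/√(1 − R²). Equivalently, 75 women act like 75/(1 − R²).

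| Assumed R² | 75/(1 − R²) | Noncentrality | Power at Mann-Whitney efficiency | Power, linear ANCOVA, normal errors |
|---|---|---|---|---|
| 0 | 75 | 2.86 | 81.0% | 82.8% |
| 0.02 | 76.5 | 2.89 | 81.8% | 83.5% |
| 0.05 | 78.9 | 2.93 | 82.9% | 84.6% |
| 0.10 | 83.3 | 3.01 | 84.9% | 86.5% |
| 0.20 | 93.8 | 3.20 | 88.7% | 90.1% |

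The last column starts 1.8 points higher (82.8 − 81.0) because a t-type analysis is slightly more efficient than a rank test on normal data. That part is not a gain from adjustment. The standard error falls by 1 − √(1 − R²): about 2.5%, 5% and 11% at R² of 0.05, 0.10 and 0.20.

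**Step 3: how far the SD matters.** Once the starting power is fixed at 81%, the gain depends almost entirely on R²; with SD 9.9 the Mann-Whitney-efficiency figures are 80.6%, 82.5%, 84.5% and about 88% at R² of 0, 0.05, 0.10 and 0.20. If the SD of the satisfaction VAS is not near 10, the starting power itself changes. At an SD of 15, for example, the unadjusted Mann-Whitney power for a difference of 4.7 is 46%.

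**Step 4: chance imbalance.** For a continuous covariate the between-arm difference in means has standard error √(2/75) = 0.163 SD. A gap of at least 0.2 SD (z = 0.2/0.163 = 1.22) therefore occurs in about 22% of trials. This is ordinary sampling variation, which adjustment removes to the extent that the covariate is prognostic.

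**The case against.** The strongest reply is that nothing here is an error. An unadjusted rank test holds its type I error under randomisation. A reader might infer that imbalance in catastrophizing or labor onset would bias the result. It would not: random imbalance is already reflected in the test's error rate. That reply stands.

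A reader might also infer that the plan assigns the Mann-Whitney test to satisfaction, or to pain. The documents do not support this. The power statement names no endpoint, so the link to satisfaction rests only on satisfaction being primary, and no test is assigned to pain at all.

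The size of the gain is also open to challenge. Neither VAS has its own baseline, which is usually the strongest covariate, and the protocol gives no correlation between the collected measures and either outcome. The 1/(1 − R²) rule belongs to linear models. It does not strictly apply to a proportional-odds model, whose adjusted odds ratio is a different quantity from the unadjusted one and from the mean difference of 4.7 that was powered. These points also stand, so the power figures are illustrations only.

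Finally, STUDY ENDPOINTS asks about a companion's presence when the woman wants it. Preference entered only as a main effect averages over women who do and do not want a companion, and does not answer that question. In the BACKGROUND survey 29 of 34 (85%) would have chosen a companion, so preference may vary little as a predictor.

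None of this removes the core. Usable pre-randomisation covariates are collected from every woman, and no adjusted analysis is specified.

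**Conclusion.** The point holds as a missed efficiency and an unspecified analysis. The documents do not support calling the Mann-Whitney test invalid or the 81% wrong. Read as the test for the satisfaction VAS, it is sound but leaves prognostic data unused.

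The likely benefit runs from nothing to about 8 points of power (81.0% to 88.7%) as R² goes from 0 to 0.20, with about 2 points at 0.05 and 4 at 0.10. This rests on a back-solved SD, on assumed R² values and on a linear-model approximation. If the covariates do not predict the outcome, the cost is about 3 to 4 of 148 degrees of freedom. The downside is small and the data are already being collected, so the change is worth making, with moderate confidence in its value.

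**What to change.** Add a short statistical analysis section, written before outcome data are examined by arm, that does the following:

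- Names the endpoint, scale and SD behind the 4.7.
- Makes the primary analysis a covariate-adjusted comparison of the satisfaction VAS by arm: ANCOVA, or a rank-based or ordinal regression if the VAS is skewed. The rule for choosing between them should be fixed in advance and applied to the data pooled over arms.
- Fixes a short covariate list: pre-procedure STAI, Pain Catastrophizing Scale and labor onset (induced or spontaneous), plus one scored expectations item if its scoring is defined beforehand. Labor onset does not appear in the list of collected data, so its recording at screening should be stated.
- Reports the arm effect with its 95% CI.
- Uses the same model for the pain VAS.
- Keeps the unadjusted Mann-Whitney test as a sensitivity analysis.

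Maternal preference may be added as a covariate. The question about women who want a companion still needs its own stated analysis, because a main effect for preference does not supply one.

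The cost is a few paragraphs of plan text and a commitment to the covariate list in advance. It needs no extra participants and no new questionnaires.

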Parturients will be included if they are delivering the first child and are planning to labor with neuraxial analgesia. Additionally, there will need to be sufficient time before delivery to allow the completion of the Pre procedure questionnaire, State-Trait Anxiety

Inventory (STAI) questionnaire both before and after the procedure, as well as the Newest Vital Sign questionnaire and the Pain Catastrophizing Scale questionnaire before the procedure. They will be included if they are ASA 2. Furthermore, they be required to read and comprehend the English language, as the Newest Vital Sign questionnaire requires them to read and interpret a nutrition label.

Physician Inclusion:

Anesthesiology Attending, Fellow or Resident Physicians who participants in the placement of the epidural catheter placement

Companion Inclusion:

Primary companion identified by parturient over the age of 18

Exclusion: Parturients will be excluded if they are receiving neuraxial anesthesia for a cesarean delivery, external cephalic version, or other non-labor procedure. They will also be excluded if they begin to push for delivery before completion of the STAI questionnaire following labor epidural catheter placement. They will be excluded if there is no support person present at the time of the neuraxial procedure. They will be excluded if they are ASA 3 or greater, or if they have a contraindication to receiving any of the medications routinely used in the placement of a labor epidural catheter (lidocaine, bupivacaine, epinephrine, fentanyl). Adults who are unable to consent and minors will be excluded.

STUDY-WIDE NUMBER OF PARTICIPANTS:

The total number of participants has been determined to be 75 per group, for a total of 150.

STUDY-WIDE RECRUITMENT METHODS:

Potential participants will be recruited while they are on the labor and delivery ward at Prentice Women's hospital, prior to the placement of a labor epidural catheter. They will be approached by a member of the research team.

Potential participants will be identified by interview and personal history, as well as by anesthesia and obstetric notes in the electronic medical record.

No advertisements will be used to recruit participants for the study.

MULTI-SITE RESEARCH:

N/A

STUDY TIMELINES:

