The duration of an individual's participation extends from initial enrollment while on the labor and delivery ward prior to labor epidural catheter placement until the completion of the STAI questionnaire and survey following this procedure. The duration of the study enrollment is anticipated to be 3-5 months, with the plan to enroll an average of 2-4

parturients daily, and accounting for study drop-outs. The estimated date for study completion is late spring to early summer of 2017.

STUDY ENDPOINTS:

The primary endpoint for the study is:

- Does having a support person present when it is the desire of the parturient has a positive effect on maternal satisfaction during the placement of epidural catheter for labor analgesia?

The secondary endpoints are:

- Does having a support person present when it is the desire of the parturient has a positive effect on maternal anxiety during the placement of epidural catheter for labor analgesia?
- Does having a support person present when it is the desire of the parturient have a positive effect on maternal perception of pain during the placement of epidural catheter for labor analgesia?
- Does the presence of a support person affect the perceived difficulty of the procedure by the provider placing the labor epidural catheter?
- Does the level of health literacy of a parturient affect her level of anxiety?
- Does the degree of Pain Catastrophizing affect the parturients level of anxiety?
- Does the relationship of the parturient to the support person have an effect on the level of anxiety of the parturient?
- Does the ethnicity of the parturient have an effect on the level of anxiety?
- Does induction of labor versus spontaneous labor have an effect on the level of anxiety of the parturient?

PROCEDURES INVOLVED:

Parturients who have been admitted to the Labor and Delivery ward at Prentice Women's Hospital will be approached by a member of the research team prior to the placement of a labor epidural catheter. They will be asked if they are considering neuraxial labor analgesia, and if they are they will be screened using the inclusion and exclusion criteria to determine study eligibility. Once they have been evaluated and found to be appropriate for the study, they will be invited to participate.

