The provider will place the labor epidural catheter in the regular fashion, as is common practice at Prentice Women's Hospital. After preparation and draping of the skin in the sitting position, infiltration with Lidocaine 1% will be conducted at L3-L4 or L4-L5. A 17g Tuohy needle will be advanced into the epidural space, using a loss of resistance with either saline or air, depending on the provider's preference. After the epidural space has been located, a 27g pencil-tip spinal needle will be placed through the Tuohy, into the intrathecal space, and an intrathecal dose of medication will be administered. The exact dose to be injected will be left up to the discretion of the provider, who will determine the appropriate dose based on the patient's situation at that time. After the intrathecal dose is administered, the spinal needle will be removed and a 19g epidural catheter will be placed through the Tuohy into the epidural space. It will be secured at the skin with a sterile dressing and tape, leaving 5cm of the catheter in the epidural space. The patient will then be placed in a lateral position.

After the completion of the neuraxial procedure, the study participant will be asked to record her overall satisfaction with the procedure, as well as her perception of pain during the placement of the labor epidural catheter, using two VAS from 0-100mm. Additionally, she will be asked to complete the STAI questionnaire again. Finally, she will be asked to complete the post procedural questionnaire. At that point the parturient's participation in the study will be complete.

The provider or research team member will be asked to fill out the Participant's Demographics Information form.

The provider placing the labor epidural catheter will be asked to evaluate his/her ability to palpate landmarks for placement, the positioning of the patient, and overall perceived difficulty with the epidural placement, using a VAS from 0-100mm for each, which will be kept confidential. Additionally, they will complete a short series of questions focusing on

the presence of a companion for the procedure. No identifying information from the provider will be recorded on this form.

DATA AND SPECIMEN BANKING:

N/A

DATA AND SPECIMEN MANAGEMENT:

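### The plan gives the secondary anxiety endpoint no analysis and no role for baseline STAI; a baseline-adjusted model would gain precision at no data cost

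*Combined protocol and SAP*

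**What the plan says.** Under PROCEDURES INVOLVED, the parturient first completes the STAI, before she knows her group. The other baseline forms follow. Her own wish is then recorded: "she will be asked for her preference with regard to the presence of a support person". Randomization comes next: "After all these data have been collected, the parturient will be randomized". After the epidural, "Additionally, she will be asked to complete the STAI questionnaire again". Satisfaction and pain are described only as ratings made after the procedure ("the study participant will be asked to record her overall satisfaction with the procedure"), so they have no baseline value.

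Under STUDY ENDPOINTS, the first secondary question is "Does having a support person present when it is the desire of the parturient has a positive effect on maternal anxiety". OBJECTIVES frames anxiety differently, predicting no significant improvement when everyone is included.

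The one statistical statement is the power sentence under DATA AND SPECIMEN MANAGEMENT: 75 per group, 81% power, a mean difference of 4.7, alpha 0.05, "using a two-sided Mann-Whitney-Wilcoxon Test". It names no outcome, standard deviation or covariate. The same section lists "STAI forms before and after epidural placement" as data collected, without defining an analysis variable.

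Some women may leave after randomization. INCLUSION AND EXCLUSION CRITERIA excludes those who begin pushing before the second STAI is complete. PROCEDURES INVOLVED and WITHDRAWAL OF PARTICIPANTS remove those whose companion breaks the rules. Their place in the arm comparison is not stated.

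**The concern.** The plan collects a pre-randomization value of the outcome it will later compare, but does not say how to use it. Three analyses are open: post-procedure score alone, change from baseline, or post-procedure score adjusted for baseline. They estimate the same arm difference with different precision. If the one named test were carried over to anxiety by default, information already paid for would be discarded. If change were used because two forms exist, the result could be less precise than ignoring baseline altogether.

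No endpoint in this document has a stated analysis. STAI is singled out because it is the arm-compared outcome for which the document describes a baseline value of the same measure, so a specific, better method is available now.

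The population matters too. The endpoint concerns women who want a companion, whereas OBJECTIVES speaks of all participants. Leaving both population and method open also allows the anxiety result to be chosen after the data are seen.

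**Working it through.** **The plan's own figure.** The stated 81% power cannot be reproduced, because no SD is given. Solving backwards with 75 per arm, a difference of 4.7 and two-sided alpha 0.05 gives an SD of about 9.9 (normal approximation, Mann-Whitney efficiency 3/π). At SD 10 the same method gives 80.3%. This shows the figure is attainable, but not that it refers to STAI.

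**Inputs.** From the documents: 75 per arm (NUMBER OF LOCAL PARTICIPANTS), alpha 0.05 (power sentence), and 29 of 34 surveyed women wanting a companion (BACKGROUND). Assumed: r = 0.3, 0.5 or 0.7; SD 10; normal scores; a linear relation between scores; a true difference of 3 points as illustration. The change-score factors also assume equal SDs before and after.

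**Variance of the arm difference relative to post-procedure score alone** (these factors do not depend on the SD):
- Baseline-adjusted: 1 − r².
- Change score: 2(1 − r).
- Equivalent sample size per arm when adjusted: 75/(1 − r²).

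| r | Adjusted | Equivalent n per arm | Change score |
|---|---|---|---|
| 0.3 | 0.91 | 82.4 | 1.4 |
| 0.5 | 0.75 | 100 | 1.0 |
| 0.7 | 0.51 | 147.1 | 0.6 |

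If the SDs differ, with k = baseline SD / post-procedure SD, the change-score factor is 1 + k² − 2rk. At k = 0.7 it is 1.07, 0.79 and 0.51. The adjusted factor is unchanged and is never the larger of the two.

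**In points, at SD 10.** 95% CI half-width = t × SD × √(factor) × √(2/n). Unadjusted with 75 per arm: 1.976 × 10 × √(2/75) = 3.23. Miss rate is the chance of not detecting a true 3-point improvement (noncentral t).

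| Analysis, 75 per arm | Half-width | Miss rate |
|---|---|---|
| Post score, t-test | 3.23 | 55% (Mann-Whitney 57%) |
| Adjusted, r = 0.3 / 0.5 / 0.7 | 3.08 / 2.79 / 2.30 | 52% / 44% / 28% |
| Change, r = 0.3 / 0.5 / 0.7 | 3.82 / 3.23 / 2.50 | 66% / 55% / 35% |

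The unadjusted half-width is 2.6 at SD 8 and 4.8 at SD 15. Adjustment gives 2.5, 2.2 or 1.8 and 4.6, 4.2 or 3.5 respectively.

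**Women who wanted a companion.** 29/34 = 0.853, and 0.853 × 75 = 64 per arm. The exact 95% interval for the share is 69% to 95%, or 52 to 71 per arm. With 64 per arm and SD 10, the half-width is 3.50 unadjusted and 3.34, 3.03 or 2.50 adjusted. The miss rate is 61% unadjusted and 58%, 51% or 35% adjusted.

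**Cost of leaving the choice open.** With no true effect (4,000 simulated trials per r), taking the best of post-score Mann-Whitney, change-score Mann-Whitney and the adjusted model gives about 9% to 10% false positives in all participants. Choosing between the two populations as well gives about 12% to 13%. The nominal rate is 5%.

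**The case against.** A reader might infer that the plan has chosen an unadjusted Mann-Whitney test for anxiety. The documents do not support this: the test appears only in a power sentence that names no outcome, and the primary endpoint is satisfaction. The gap is silence about anxiety, and the unadjusted figures above are only a reference point.

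A reader might also infer that an unadjusted result would be biased. It would not be, because baseline STAI and randomization come in the right order. Only precision and the open choice are at issue.

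The precision gain depends on an r and SD that the documents do not give. A low r is plausible, since the second form follows an intrathecal dose and the first may be completed well before it. At r = 0.3 the half-width moves only from 3.2 to 3.1. This stands, and so does the dependence of the change-score factors on equal SDs.

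It would be too strong to call the choice of state or trait score wholly open. STUDY ENDPOINTS asks about anxiety during placement, and PROCEDURES INVOLVED uses the form to gauge anxiety just before it. Both point to the state score, so a confirming sentence is enough.

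The estimate of 64 per arm is soft. The survey is not said to be limited to first births, and it included women who already had a catheter.

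Finally, anxiety is secondary, and every endpoint lacks a stated analysis. That limits the weight of the point but does not remove an improvement that costs nothing to adopt.

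**Conclusion.** The point holds as a free improvement to a secondary endpoint. The plan measures STAI before randomization and again after placement, but gives anxiety no analysis. Baseline adjustment would cut the variance of the arm difference by 9%, 25% or 49% at r = 0.3, 0.5 or 0.7, given a roughly linear relation between the scores. The proportional gain does not depend on the SD; the figures in points assume SD 10. A change score is not a safe substitute: with equal SDs it loses to ignoring baseline whenever r is below 0.5. The documents do not show that an inferior test was chosen or that the result would be biased, and the primary satisfaction endpoint is untouched. The change should be made before the data are seen.

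**What to change.** State the main anxiety analysis as a linear model of the post-procedure STAI state score (the sponsor to confirm the scale) on randomized arm and the baseline score of the same scale. Report the adjusted difference with its 95% CI. Keep Mann-Whitney as a sensitivity analysis, and do not use the change score as the main measure.

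Name the population for each question in advance:
- for the STUDY ENDPOINTS question, women whose recorded pre-randomization preference was to have a companion, compared between randomized arms;
- for the OBJECTIVES hypothesis, all randomized participants with a post-procedure STAI.

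Report by arm how many were removed after randomization and why, including those who began pushing before the second form. Say which result answers which question. OBJECTIVES predicts a non-significant result but sets no decision rule, so interpret a null finding through its CI and not as evidence of no improvement.

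The cost is a few sentences of text; both STAI forms and the preference form are already collected. The downsides are a small gain if r is near 0.3, reliance on a roughly linear relation between the scores, and fewer women in the preference-based comparison (about 64 per arm if the survey share applies).
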